9.5. Study size

All pregnancies among women who meet the study inclusion/exclusion criteria will be included in this study.

As the IC conditions included are heterogeneous and the number of MCMs for the primary outcome is likely small, the prevalence of each MCMs among each IC condition under study is not available. For sample size calculation for the cohort study, we employed the prevalence of overall MCMs (3%) in the general population [Holmes, 1976; Leppig, 1987; Marden, 1964; Van Regemorter, 1984] which might have a lower prevalence than among women with IC conditions. Therefore, the sample size calculated is relatively conservative. Assuming a 1:3 ratio of HZ/su-exposed to unexposed, a type 1 error of 0.05, and a target risk ratio of 2.0 for the primary safety outcome of MCMs, 711 live birth infants (live birth pregnancies linked to infant records) from the HZ/su-exposed group and 2133 live birth infants from the unexposed group will allow us to achieve 90% power.

The Power Analysis and Sample Size software (NCCS Statistical Software) was used in the sample size calculation.

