9.7.2. Cohort Study

If the feasibility assessment (Section 9.6.1.1) identifies that the number of HZ/su-exposed pregnancies is equal to or above the target number of exposed pregnancies, a subsequent cohort study will be conducted.

Infant/birth outcomes and pregnancy complications will be assessed among eligible live birth pregnancies linked to infant records. Pregnancy outcomes will be assessed in the population of all pregnant women meeting eligibility criteria.

Propensity scores and matching will occur within each Data Partner. Potential confounders are described in Section 9.3.3. The methodology will be described in detail in the Statistical Analysis Plan (SAP).

9.7.2.1. Primary Objective and Secondary Objective 1

The Mantel-Haenszel Chi-square test or Fisher exact test (univariate analysis), wherever appropriate, will be employed to compare the prevalence of the primary outcome (MCMs) between eligible live birth pregnancies among women with IC conditions who were vaccinated with HZ/su during pregnancy and those who were not vaccinated with HZ/su during pregnancy. Multivariable conditional logistic regression will be conducted to adjust for potential residual confounding after matching if there is statistical significance in univariate analysis. In addition, the prevalence of MCMs and their associated 95% CIs will be calculated among women with IC conditions who were exposed to HZ/su during pregnancy versus the corresponding matched women who were not exposed to HZ/su during pregnancy. All analyses will be stratified by stage of pregnancy (pre-pregnancy, first trimester, second trimester, third trimester).

Similar methods will be used for each of the secondary infant/birth outcomes (e.g., preterm birth, SGA, LBW, NICU admission, neonatal death).

9.7.2.2. Secondary Objective 2

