Pregnancy outcomes will be compared between eligible pregnancies among women with IC conditions who were vaccinated with HZ/su during pregnancy and those who were not vaccinated with HZ/su during pregnancy. Univariate and multivariable statistical analyses will be performed as stated in the primary objective and secondary objective 1 (Section 9.7.2.1) for all outcomes. The prevalence of the pregnancy outcomes (live birth, stillbirth, and spontaneous abortion) and pregnancy complications (placental abruption, preeclampsia and eclampsia) and their 95% CIs will be calculated between the two groups of women. All analyses will be stratified by stage of pregnancy (pre-pregnancy, first trimester, second trimester, third trimester).

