Annex 10 ENCePP Checklist for study protocols

Sect	ion 1: Milestones	Yes	No	N/A	Section	n Number
1.1	Does the protocol specify timelines for					
	1.1.1 Start of data collection ¹	\boxtimes				5
	1.1.2 End of data collection ²	\boxtimes				5
	1.1.3 Progress report(s)			\boxtimes		
	1.1.4 Interim report(s)			\boxtimes		
	1.1.5 Registration in the EU PAS Register®		\boxtimes			
	1.1.6 Final report of study results.	\boxtimes				5
Com	ments:					
Sect	ion 2: Research question		Yes	No	N/A	Section Number
2.1	Does the formulation of the research question and object clearly explain:	ctives	\boxtimes			4, 7, 8, 9
	2.1.1 Why the study is conducted? (e.g. to address an inpublic health concern, a risk identified in the risk management plan, an emerging safety issue)	mportant	\boxtimes			7, 8
	2.1.2 The objective(s) of the study?		\boxtimes			8
	2.1.3 The target population? (i.e. population or subgroup the study results are intended to be generalized)	o to whom	\boxtimes			8, 9.1,
	2.1.4 Which hypothesis(-es) is (are) to be tested?		\boxtimes			4, 9.5, 9.7
	2.1.5 If applicable, that there is no a priori hypothesis?				\boxtimes	
Com	ments:					

¹ Date from which information on the first study is first recorded in the study dataset or, in the case of secondary use of data, the date from which data extraction starts.

² Date from which the analytical dataset is completely available.

	tion 3: Study design	7	'es	No	N/A	Section Number
3.1	3.1 Is the study design described? (e.g. cohort, case-control, cross-sectional, other design)		\boxtimes			9.1
3.2	Does the protocol specify whether the study is based on primary, secondary or combined data collection?		\boxtimes			9.1, 9.4
3.3	Does the protocol specify measures of occurrence? (e.g., rate, risk, prevalence)	, [\leq			9.1
3.4	Does the protocol specify measure(s) of association? (e.g. risk, odd ratio, excess risk, rate ratio, hazard ratio, risk/rate difference, numb needed to harm (NNH))		\boxtimes			9.7.2
3.5	Does the protocol describe the approach for the collection and reporting of adverse events/adverse reactions? (e.g. adverse event that will not be collected in case of primary data collection)	ts [\leq			11
Com	ments:					
Sect	tion 4: Source and study populations	Yes	No	2	N/A	Section
4.1						Number
7.1	Is the source population described?	\boxtimes]		Number 9.1, 9.2

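### The protocol targets a risk ratio, but Section 9.7.2 names no between-group effect measure; its only adjusted model gives an odds ratio, and runs only after a significant test

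*Protocol*

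**What the plan says.** Section 8 frames all three objectives as comparisons of prevalence between exposed and unexposed pregnancies. Section 9.5 plans for "a target risk ratio of 2.0 for the primary safety outcome of MCMs"; the Abstract and Section 9.2.1.3 repeat that target.

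Section 9.7.2.1 lists three outputs for the primary outcome:

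- a Mantel-Haenszel chi-square or Fisher exact test;
- a model: "Multivariable conditional logistic regression will be conducted to adjust for potential residual confounding after matching", to be run only when the univariate test is significant;
- the prevalence of malformations with 95% CIs in the exposed and in the matched unexposed.

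The same section carries similar methods to preterm birth, SGA, low birth weight, NICU admission and neonatal death. Section 9.7.2.2 carries them to live birth, stillbirth, spontaneous abortion, placental abruption, preeclampsia and eclampsia: "Univariate and multivariable statistical analyses will be performed as stated in the primary objective and secondary objective 1".

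Item 3.4 of the ENCePP checklist in Annex 10 asks "Does the protocol specify measure(s) of association". It is ticked Yes with a reference to 9.7.2. No risk ratio, risk difference or odds ratio is named there.

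**The concern.** The planning target is on one scale and the only adjusted estimate is on another, and the section that should state the reported measure does not. Conditional logistic regression estimates a conditional odds ratio. That is close to the risk ratio when the outcome is rare and departs from it as the outcome becomes common.

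The significance condition adds to this. If the univariate test is not significant, the listed outputs are a test result and two separate prevalences. No ratio or difference with an interval is specified to show which effects the data can and cannot exclude. If the test is significant, the only modelled contrast is an odds ratio.

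At stake is how the secondary results of a vaccine pregnancy-safety study are read. A reader told to expect a risk ratio may take an odds ratio for one and find that it does not match the two prevalences printed beside it.

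**Working it through.** **1. The plan's own figure.** The inputs come from Section 9.5. The baseline is given there as "we employed the prevalence of overall MCMs (3%) in the general population". Three unexposed infants are planned per exposed infant, alpha is 0.05, the target ratio is 2.0 and power is 90%. The protocol does not state the sidedness of the test; two-sided is assumed. The formula for the exposed group, with k = 3 unexposed per exposed, is

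n = [z(0.975) × √(p̄(1−p̄)(1+1/k)) + z(0.90) × √(p1(1−p1) + p0(1−p0)/k)]² / (p1−p0)², with p̄ = (p1 + k·p0)/(1+k).

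- Reading 2.0 as a risk ratio: p1 = 0.06, p0 = 0.03, n = 641. The stated figure is 711.
- Reading 2.0 as an odds ratio: the odds are 2 × 0.03/0.97 = 0.0619, so p1 = 0.0619/1.0619 = 0.05825 (risk ratio 1.94), and n = 711.

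The alternatives in Section 9.2.1.3 behave the same way:

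| Ratio | Stated exposed | Odds ratio 2.0 | Risk ratio 2.0 |
|---|---|---|---|
| 1:3 | 711 | 711 | 641 |
| 1:2 | 812 | 812 | 733 |
| 1:1 | 1108 | 1109 | 1002 |

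So the figures labelled as for a risk ratio match an odds ratio of 2.0. The slip is conservative: 711 and 2133 give 92.5% power for a true risk ratio of 2.0. It is a separate labelling point, but it shows that the two scales are already mixed in this document.

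**2. What the chosen scale does to each outcome.** With p1 = RR × p0, OR = [p1/(1−p1)] / [p0/(1−p0)]. Only the 3% comes from the protocol; the other prevalences are assumptions, shown as ranges.

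| Outcome coded | p0 | RR | Calculation | OR |
|---|---|---|---|---|
| Malformation | 3% | 2.0 | (0.06/0.94)/(0.03/0.97) | 2.06 |
| e.g. preterm or NICU | 10% | 1.5 | (0.15/0.85)/(0.10/0.90) | 1.59 |
| e.g. preterm or NICU | 20% | 1.5 | (0.30/0.70)/(0.20/0.80) | 1.71 |
| Live birth | 80% | 0.90 | (0.72/0.28)/(0.80/0.20) | 0.64 |
| Live birth | 90% | 0.90 | (0.81/0.19)/(0.90/0.10) | 0.47 |

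These are marginal conversions; a conditional odds ratio may lie further from 1.

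**3. The live-birth rows recoded as loss.** Section 9.2.1 excludes ectopic and molar pregnancies and induced abortions, so in the Secondary Objective 2 cohort a pregnancy that is not a live birth is a stillbirth or a spontaneous abortion.

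- Live birth falling from 90% to 81% is loss rising from 10% to 19%: RR 0.19/0.10 = 1.90, OR (0.19/0.81)/(0.10/0.90) = 2.11.
- Live birth falling from 80% to 72% is loss rising from 20% to 28%: RR 0.28/0.20 = 1.40, OR (0.28/0.72)/(0.20/0.80) = 1.56.

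Coded as loss, the odds ratio exceeds the risk ratio by about 11% in both cases (2.11/1.90 and 1.56/1.40).

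**4. The matched risk ratio and the planned prevalences.** The Mantel-Haenszel risk ratio over matched sets is Σ(a·n0/N)/Σ(b·n1/N), where a and b are the exposed and unexposed events in a set. In complete 1:3 sets n1 = 1, n0 = 3 and N = 4, so it equals 3A/B, with A and B the event totals. With S sets this is (A/S)/(B/3S), the ratio of the two group prevalences. It therefore agrees with the planned prevalences when all sets are complete. What they lack is a named contrast and an interval for it.

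**The case against.** Several parts of the opposing case stand.

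- A reader might infer that the odds ratio is the only result the plan produces. It is not: prevalences with 95% CIs are planned for both groups, and a crude risk ratio follows from them. What is missing is a named contrast with its interval.
- A reader might infer that every outcome will receive an odds ratio. The model is specified for every outcome but run only after a significant univariate test.
- A reader might infer that effects on common outcomes will be overstated. An odds ratio is not biased because the outcome is common. It misleads only if taken for a risk ratio, and the protocol nowhere says it will be reported as one.
- A reader might take 0.47 against 0.90 for live birth as a hidden doubling of harm. The size of that contrast comes from coding the outcome as live birth; coded as loss, the gap is about 11%.
- The sample-size figures fit the odds-ratio scale, so the contrast between sizing and model lies in the stated target, not in the numbers.

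It is also argued that the reporting scale is detail for the SAP, to which Sections 9.7.2 and 9.7.4 defer and which was not available here. It may well name a risk ratio there. That does not remove the point: the protocol itself fixes the model and the condition for running it, and its checklist states that the measure is given in 9.7.2, where it is not.

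Lastly, conditional logistic regression is a standard model for matched sets, and Sections 9.3.3, 9.3.3's discussion of distributed regression, and 9.7 tie the work to distributed tools. This stands as a reason not to require its replacement.

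**Conclusion.** The point holds as a gap in the reported contrast and a mismatch of scale. The protocol states a risk-ratio target and prevalence comparisons, names no effect measure where its checklist says it does, and offers one adjusted model that yields an odds ratio on condition of significance.

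For the primary outcome the scale is immaterial (2.06 against 2.0 at the protocol's 3%). For outcomes at an assumed 10-20% it is modest (1.59-1.71 against 1.5). It is largest if live birth is the coded outcome (0.64-0.47 against 0.90 at an assumed 80-90%). Apart from the 3%, these sizes rest on prevalences the protocol does not give. The documents support no claim of bias in the odds ratio. The change is worth making, but the primary conclusion does not hang on it.

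**What to change.** In Sections 9.7.2.1 and 9.7.2.2, name two effect measures for every outcome, reported whether or not the univariate test is significant and beside the planned prevalences:

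- the matched risk ratio (Mantel-Haenszel over matched sets) with a 95% CI;
- the risk difference with a 95% CI.

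Keep conditional logistic regression as the adjusted analysis and label its estimate an odds ratio. Modified Poisson regression, with robust variance clustered on matched set, is an optional addition that gives an adjusted risk ratio where the distributed tools allow it. Checklist item 3.4 will then be correct as it stands. In the same edit, reconcile the risk-ratio label in the Abstract and in Sections 9.2.1.3 and 9.5 with the calculation behind 711, 812 and 1108.

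The cost is wording and a little more analysis work. For a rare outcome such as neonatal death, a group with no events may leave the risk ratio inestimable, and the risk difference then carries the comparison. Modified Poisson, if added, may need shared matched-set data or a distributed routine, which is why it is optional.

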9.2.1.2. HZ/su-Exposed Group (Amended 15 August 2022)

Among the eligible cohort of live birth pregnancies linked to an infant (Primary Objective and Secondary Objective 1 cohort) and among the cohort of all eligible *live birth and non-live birth* pregnancies (Secondary Objective 2 cohort), women with IC conditions exposed to HZ/su during pregnancy will be identified. Exposure will be further categorized by stage of pregnancy: pre-pregnancy, first trimester, second trimester, and third trimester. The first trimester of pregnancy will be defined as 0 to < 14 weeks gestation, the second trimester as 14 to < 28 weeks, and the third trimester as 28 weeks through the end of the pregnancy.

A 30-day pre-pregnancy period (prior to LMP) will be included. There is no safety signal that would indicate that there is a risk pre-pregnancy. However, published vaccine safety studies have included varying pre-pregnancy periods [Kerr, 2020, Kharbanda, 2021, Panagiotakopoulos, 2020]. More recently published studies have included no pre-pregnancy or up to a 42-day pre-pregnancy period.

214420 (EPI-ZOSTER-039 VS US DB) Protocol Amendment 2 Final

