9.3. Variables

9.3.1. Exposure

Among the eligible cohort of live birth pregnancies linked to an infant (Primary Objective and Secondary Objective 1 cohort) and among the cohort of all eligible live birth and non-live birth pregnancies (Secondary Objective 2 cohort), HZ/su exposure will be defined as receipt of at least one dose of HZ/su during pregnancy. HZ/su vaccination will be identified by means of CPT code 90750 and National Drug Code (NDC) codes 58160-828-01, 58160-829-01, 58160-819-12, 58160-828-03, 58160-829-03, and 58160-823-11. We may include additional codes for identification of HZ/su exposure if relevant codes become available in the future. Pregnancies among women receiving at least one dose of HZ/su during pregnancy will be considered exposed. If a woman receives the vaccine before the start of pregnancy but does not receive the vaccine during the 30-day pre-pregnancy period or during pregnancy, she will not be considered exposed and would be considered for the comparator unexposed group. As described in Section 9.2.1.2, exposure will be further categorized by stages of pregnancy: pre-pregnancy, first trimester, second trimester, third trimester.

214420 (EPI-ZOSTER-039 VS US DB) Protocol Amendment 2 Final

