9.3.2. Outcomes (Amended 15 August 2022)

Outcomes to be evaluated include MCMs and additional infant/birth outcomes (preterm birth, SGA, LBW, NICU admission and neonatal death), complications of pregnancy (placental abruption, preeclampsia and eclampsia) and pregnancy outcomes (live birth, non-live birth [stillbirth and spontaneous abortion]). The primary outcome of this cohort study is MCMs of the infants.

As indicated in Section 9.2.1., the IC diagnoses of pregnant women and pregnancy outcomes will be identified from the health plan claims of the DRN containing ICD-10-CM Codes for IC conditions *and validated coding algorithms for IC conditions* during the period 273 days prior to the pregnancy start date through the first trimester (98 days after the pregnancy start date).

MCMs will be confirmed through chart review. Other outcomes will not be confirmed through chart review. Many of these ICD-10-CM algorithms for the secondary outcomes have not yet been validated. We will conduct a literature search prior to final analysis to determine potential validated algorithms for these secondary outcomes. Recent published studies provide evidence of the validity of ICD-10-based algorithms to identify adverse pregnancy outcomes. An international study reported moderate to high PPVs for ICD-10 codes for select secondary outcomes proposed in this study: 76.4% for LBW; 70.4% for SGA; 81.2% for preeclampsia [Watson, 2021].

Another recently published study in a US population reported higher PPVs for ICD-10-CM codes for preeclampsia and eclampsia (ranging from 89-100%) [Labgold, 2021]. In addition, an ongoing Sentinel COVID-19 pregnancy study, used ICD-10-CM codes to identify adverse pregnancy outcomes including preeclampsia/eclampsia, SGA and LBW. These algorithms were approved by the FDA team in the Hua 2021 study. Pregnancy episodes ending in a non-live birth pregnancy outcome will be identified using validated algorithms developed through Sentinel and non-Sentinel (e.g., VSD) projects [Andrade, 2021; Naleway, 2021].

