9.3.2.2. Pregnancy Complications and Outcomes (Secondary Objective 2)

The pregnancy outcomes to be evaluated include live birth, non-live birth (stillbirth, and spontaneous abortion). A stillbirth is defined as a spontaneous (non-deliberate) fetal death that occurs at or after 20 weeks' gestation but prior to delivery. A spontaneous abortion is defined as a spontaneous (non-deliberate) embryonic or fetal death that occurs prior to 20 weeks' gestation. Placental abruption (ICD-10-CM O45.X) will be identified by searching the mother's claims from 20 weeks gestation through the date of delivery. Preeclampsia and eclampsia (ICD-10-CM O11.X, O14.X, O15.X) will be identified by searching the mother's claims from 20 weeks gestation through the date of delivery. A prior study conducted at one U.S. hospital found that the sensitivity of preeclampsia and eclampsia inpatient codes are generally low, however the PPV and specificity were high [Labgold, 2021].

Pregnancy outcomes will be identified in claims data through diagnosis and procedure codes (Appendix E. Live Birth Diagnosis and Procedure Codes and Appendix H. Spontaneous Abortion and Stillbirth Codes). Pregnancy episodes resulting in a live birth will be identified using validated algorithms (see Section 9.2.1.1) that have been used in Sentinel and non-Sentinel projects [Andrade, 2012; Andrade, 2016; Johnson, 2013; Sentinel Initiative, 2018]. Pregnancy episodes ending in a non-live birth pregnancy outcome will be identified using algorithms developed through Sentinel and non-Sentinel (e.g., VSD) projects [Andrade, 2021; Naleway, 2021].

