9.7.3. Descriptive Analysis

If the feasibility assessment (Section 9.6.1.1) identifies that the number of HZ/su-exposed live birth pregnancies identified during the feasibility assessment is less than one third of the number of HZ/su-exposed live birth pregnancies needed for the cohort study, a descriptive analysis will be conducted among all HZ/su-exposed pregnancies and their matched comparators. Prevalence and 95% CIs of MCMs and additional infant/birth, complications of pregnancy, and pregnancy outcomes will be estimated in the matched HZ/su-exposed and unexposed cohorts. Additional analyses will not be conducted.

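### Spontaneous-abortion prevalence includes pregnancies first vaccinated at or after 20 weeks, which can no longer have the event; this dilutes the absolute figure equally in both groups and leaves the ratio unchanged

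*Protocol*

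**What the plan says.** - **Outcome.** Protocol 9.3.2.2 defines spontaneous abortion as an "embryonic or fetal death that occurs prior to 20 weeks" and stillbirth as a "fetal death that occurs at or after 20 weeks".
- **Exposure.** Protocol 9.3.1: "HZ/su exposure will be defined as receipt of at least one dose of HZ/su during pregnancy". Section 9.2.1.2 adds a 30-day pre-pregnancy period. It puts the first trimester at under 14 weeks, "the second trimester as 14 to < 28 weeks, and the third trimester as 28 weeks through the end of the pregnancy".
- **Estimate.** Section 9.7.2.2 gives "The prevalence of the pregnancy outcomes (live birth, stillbirth, and spontaneous abortion" with 95% CIs in the two groups, over all eligible pregnancies. It adds that all analyses are stratified by stage of pregnancy.
- **Comparators.** Section 9.2.1.3 requires an unexposed pregnancy to have reached the gestational week of its match's exposure without spontaneous abortion or stillbirth.
- **Fallback.** If too few exposed live births are found, 9.7.3 estimates the same prevalences among all exposed pregnancies and their matched comparators. It names no split by stage and closes with "Additional analyses will not be conducted".
- **Window.** Section 9.3.2 says that "the IC diagnoses of pregnant women and pregnancy outcomes will be identified from the health plan claims of the DRN" in a period running from 273 days before pregnancy start to day 98.

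**The concern.** A woman first vaccinated at 20 weeks or later has already passed the point at which a loss could be classed as a spontaneous abortion. Her comparators have reached the same gestational week without loss, so the same is true of them. These matched sets add to the denominator and nothing to the numerator.

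Section 8 states Secondary Objective 2 as assessing the prevalence of these outcomes, so the absolute figure is a result in its own right. On the descriptive path it is the whole result, because no statistical comparison is made there. That path is a real prospect: Sections 7 and 9.6.1 expect few exposed pregnancies, and the cohort study goes ahead only if at least 237 are found in the feasibility period.

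**Working it through.** The protocol gives no spontaneous-abortion risk, no distribution of dose timing and no sample size for this objective. There is no stated figure to reproduce. What follows uses its definitions plus labelled assumptions.

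**1. Which strata contain pregnancies at risk?** 14 weeks = 98 days, 20 weeks = 140 days, 28 weeks = 196 days.

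| Stage of first dose (9.2.1.2) | Can a spontaneous abortion follow? |
|---|---|
| Pre-pregnancy, 30 days before LMP | Yes, throughout |
| First trimester, under 14 weeks | Yes, throughout |
| Second trimester, 14 to under 20 weeks | Yes |
| Second trimester, 20 to under 28 weeks | No |
| Third trimester, 28 weeks on | No |

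Weeks 20 to under 28 make up 8 of the 14 weeks of the second-trimester stratum (8/14 = 57%). If doses were spread evenly over that stratum (an assumption), its reported prevalence would be 6/14 = 43% of the at-risk prevalence. The third-trimester stratum is zero by definition in both groups.

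**2. Size of the dilution.** Let f be the share of exposed pregnancies first dosed at or after day 140, and p the prevalence among those dosed earlier. Then

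reported prevalence = p × (1 − f) + 0 × f = p × (1 − f).

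With a constant matching ratio and alignment on gestational week, f is the same among comparators. As an illustration, assume at-risk prevalences of 10% in comparators and 15% in exposed, and the primary-outcome group sizes (711 and 2133) for this cohort. All of these are assumptions. Power is two-sided at 0.05.

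| f | Comparators, reported | Exposed, reported | Ratio | Power, all pregnancies | Power, dosed before 20 weeks only |
|---|---|---|---|---|---|
| 0 | 10.0% | 15.0% | 1.50 | 94.0% | 94.0% |
| 0.10 | 9.0% | 13.5% | 1.50 | 91.3% | 91.7% |
| 0.30 | 7.0% | 10.5% | 1.50 | 82.9% | 84.3% |
| 0.50 | 5.0% | 7.5% | 1.50 | 69.1% | 71.7% |

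**3. The ratio.** 15(1 − f) / 10(1 − f) = 1.50 for every f, because the factor cancels. In a conditional logistic model with matched sets as strata, the late-dosed sets contain no event and contribute nothing to the likelihood, so that estimate does not move either.

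**4. The day-98 sentence.** Day 98 is 42 days before day 140. Taken literally, the sentence in 9.3.2 would admit no stillbirth and no loss between weeks 14 and 20. But it cites 9.2.1, which gives that window only to codes for immunocompromising conditions. Section 9.3.2.2 finds pregnancy outcomes through the code lists in Appendices E and H with no day-98 limit, and searches the complications from 20 weeks to delivery. The phrase conflicts with both sections and cannot be the working rule.

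**The case against.** The strongest reply is that the planned comparison is sound. Alignment on gestational week puts the zeros equally in both groups, and the reference is the matched unexposed group, diluted to the same degree. The protocol names no risk difference and plans no comparison with a background rate. All of this stands. A reader might infer that the vaccine would look falsely safe relative to no vaccine; the documents do not support that.

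Second, 9.7.2.2 stratifies by stage, and two of the four strata lie wholly before 20 weeks. This also stands for the cohort study. It does not repair the overall figure or the second-trimester stratum, and 9.7.3 provides no such split.

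Third, Section 7 expects exposure mainly in unintended pregnancies and before the woman knows she is pregnant. That points to early doses and a small f, so the rows at 0.30 and 0.50 mark a range and are not forecasts. This stands.

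Fourth, a woman dosed at week 18 carries only the residual risk to week 20, so even the restricted figure depends on dose timing and is not a background rate. This is true, and it is a reason to report by stage as well. It does not alter the factor (1 − f), since p is the average over all doses before 20 weeks.

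Fifth, at-risk denominators are often left to the SAP, which is not at hand and may address this. For 9.7.2.2 that is a fair point. Section 9.7.3, however, fixes the population as all exposed pregnancies and rules out further analyses, so the protocol is the place to correct it.

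A reader might also infer that 9.3.2 stops the search for outcomes at day 98. Sections 9.2.1 and 9.3.2.2 show that it does not in effect.

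**Conclusion.** The point holds for the absolute prevalence of spontaneous abortion and its CI: in the overall analysis, in the second-trimester stratum and in the descriptive analysis of 9.7.3. Both groups are understated by the same factor (1 − f). With f = 0.10 and an assumed 10% risk the reported figure is 9%; it would fall to 5% only if half the doses came at or after 20 weeks. Both f and the risk are assumptions, and the protocol's own account of likely exposure suggests that f is small.

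It would go too far to say that the Secondary Objective 2 prevalences in general are wrong. Live birth and stillbirth remain possible after a dose at or after 20 weeks, the complications have their own windows to delivery, and the between-group ratio for spontaneous abortion is intact. The correction is modest and cheap, and it bears on a quantity that the objective asks for. The conflict in 9.3.2 is a drafting error.

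**What to change.** For spontaneous abortion only:

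1. In 9.7.2.2, restrict the prevalence, CI and test to pregnancies whose first dose in the exposure window falls before 20 weeks 0 days, with their matched comparators.
2. In 9.7.3, apply the same restriction to the prevalence and CI, and show the figure by stage of exposure. The closing sentence of that section needs to allow this.
3. For this outcome, end the second-trimester stratum at 20 weeks and omit the third-trimester stratum.

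Editorial: in 9.3.2, remove the mention of pregnancy outcomes from the 273-day/98-day sentence, so that the windows in 9.3.2.1 and 9.3.2.2 apply without conflict.

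The cost is protocol wording and a filter on dose date, which is already needed to assign the stage of exposure. The denominator for this outcome shrinks slightly, losing only pregnancies that could not have the event. In the illustration above, power does not fall. On the descriptive path the stage-specific counts may be small, so their intervals will be wide.
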